7.3 Guidelines for Recording and Attribution Scoring of Adverse Events

Timely and complete reporting of all AEs is required for all patients. Monitoring and documentation of all AEs allows for identification of potential study-drug or dose-related AEs, and for adherence to regulatory requirements. Please refer to the CRF Completion Guidelines located in the study binder for detailed instructions for AE reporting.

7.3.1 Recording of Adverse Events

All AEs that occur from the first dose of study treatment through 30 (± 5) days after the last dose of study treatment is administered are to be recorded on the AE CRF. From the time the study Informed Consent is signed through the first dose of study drug administration, all SAEs are to be recorded. In addition, SAEs that occur after 30 (± 5) days after the last dose of study treatment where a causal relationship with the study drug is suspected will also be recorded on the AE CRF.

The resolution of all AEs must be routinely recorded and be reconciled at the end of the study. The following conventions will be followed when patient completes or discontinues from the study:

- If a patient dies, the date of death should be the date of AE stop for all ongoing AEs at the time of death.
- If a patient discontinues due to an AE(s), the outcome of the AE is to be followed for 30 (± 5) days from the date of discontinuation or until the AE has returned to Grade ≤ 1 . The status of the AE and the date of last contact with the patient will be captured. If the AE has not returned to Grade ≤ 1 by the end of the study, the AE stop date should be left as ongoing.

All AEs will be classified by intensity/severity (**Section 7.3.2**), relationship to study drug (**Section 7.5**), and as serious or non-serious (**Section 7.7**) by the Investigator.

7.3.2 Grading of Adverse Events

This study will utilize the NCI CTCAE Scale, Version 5.0 for AE grading.

7.4 Follow-up of Adverse Events

All AEs and significant abnormal laboratory values are to be followed up in accordance with the International Conference on Harmonization (ICH) Good Clinical Practice (GCP) guidelines, and other applicable regulatory requirements (e.g., United States [US] Code of Federal Regulations [CFR]). All AEs that are ongoing during the treatment period will be followed up for 30 (± 5) days from the date of the last dose of poziotinib.

7.5 Relationship

The Investigator must make a causality assessment and document their opinion as to the relationship of all AEs and SAEs to study treatment (**Table 3**).

Table 3 Investigator Assessment of Adverse Event Causality

Relationship	Description
Not Related	The event is clearly related to factors other than study treatment, such as the patient's clinical state, therapeutic interventions, or concomitant medications administered to the patient.
Unlikely Related	The temporal association, patient history, and/or circumstances are such that the study drug or treatment is not likely to have had an association with observed event.
Possibly Related	The event follows a reasonable temporal sequence from the time of study treatment administration, and/or follows a known response pattern to study treatment, but could have been produced by other factors, such as the patient's clinical state, therapeutic interventions, or concomitant medications administered to the patient.
Probably Related	The event follows a reasonable temporal sequence from the time of study treatment administration, and follows a known response pattern to study treatment, and cannot be reasonably explained by other factors, such as the patient's clinical state, therapeutic interventions, or concomitant medications administered to the patient.
Definitely Related	The event follows a reasonable temporal sequence from the time of study treatment administration, and follows a known response pattern to study treatment, and cannot be reasonably explained by other factors, such as the patient's clinical state, therapeutic interventions, or concomitant medications administered to the patient.

In addition, the event either occurs immediately following study treatment administration, improves on stopping study treatment, reappears on repeat exposure, or there is a positive reaction at the application site.

7.6 Expectedness

For investigational drugs, an AE is judged “expected” if its description agrees in nature and severity with the description of AEs previously noted with the study drug as detailed in the current Investigator’s Brochure. An “unexpected” AE is one for which the specificity or severity is neither consistent with the current Investigator’s Brochure nor the risk information described in the general investigational plan. The Sponsor will be responsible for assessing the expectedness of AEs.

The most common AEs associated with poziotinib treatment include:

- Diarrhea
- Rash/Dermatitis acneiform
- Stomatitis/Mucosal inflammation
- Paronychia
- Decreased Appetite
- Dry Skin
- Vomiting
- Pruritus

7.7 Serious Adverse Events

In the interest of patient care and to allow Spectrum to fulfill all regulatory requirements, any SAE, regardless of causal relationship to study treatment, is to be reported to the Sponsor within 24 hours of knowledge of the event. SAEs are defined (21 CFR 312.32, ICH of Technical Requirements for Registration of Pharmaceuticals for Human Use E2A Guideline) as those AEs that meet any of the following criteria:

- Results in death
- Is life-threatening: i.e., any event that, in the opinion of the Investigator, poses an immediate risk of death to the patient from that event
- Requires inpatient hospitalization or prolongation of existing hospitalization (excluding hospitalizations for study therapy, disease-related procedures, or placement of an indwelling catheter, unless associated with other SAEs)
- Results in a persistent or significant disability/incapacity or substantial disruption of the ability to conduct normal life functions
- Results in a congenital anomaly/birth defect
- Includes important medical events that may not be immediately life threatening or result in death or hospitalization but may jeopardize the patient or may require intervention to prevent one of the outcomes listed in this definition

Adverse events that do not meet any of the above criteria for serious should be regarded as non-serious.

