7.2 Adverse Events

An AE is defined as any untoward medical occurrence in a patient or clinical investigation patient, temporally associated with the use of a medicinal product, whether or not considered related to the medicinal product. Therefore, an AE can be any unfavorable and unintended sign (including an abnormal laboratory finding), symptom, or disease (new or exacerbated) temporally associated with the use of a medicinal product. A treatment-emergent AE (TEAE) is any AE that occurs from the first dose of study treatment until 30 (± 5) days after the last dose of study treatment.

The study will record all AEs according to the information in Section 7.3.

Examples of AEs **include**:

- Exacerbation of a chronic or intermittent pre-existing condition including either an increase in frequency and/or intensity of the condition
- New conditions detected or diagnosed after investigational product administration.
- Signs, symptoms, or the clinical sequelae of a suspected drug interaction

- Signs, symptoms, or the clinical sequelae of a suspected overdose of either investigational drug or a concurrent medication
- AEs may include pre-treatment or post-treatment events that occur as a result of protocol-mandated procedures (e.g., invasive procedures)

Abnormal laboratory results are to be recorded as AEs, if any of the following conditions are met:

- The abnormal laboratory value leads to a therapeutic intervention
- The abnormal laboratory value is considered to be clinically significant by the Investigator
- The abnormal laboratory value is predefined as an AE in the protocol or in another document communicated to the Investigator by Spectrum or designee

Examples of events that **do not** constitute AEs include:

- Medical or surgical procedures (e.g., endoscopy, appendectomy); the condition that leads to the procedure is an AE
- Situations where an untoward medical occurrence does not occur (e.g., social and/or convenience admission to a hospital)
- Anticipated day-to-day fluctuations of pre-existing disease(s) or condition(s) present or detected at the start of the study that does not worsen
- Planned and prescheduled hospitalizations and procedures
- Progressive disease

The adverse events of special interest identified with poziotinib treatment include diarrhea, skin rash, stomatitis, paronychia, and pneumonitis.

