7.7.2 Exclusions to Serious Adverse Event Reporting Requirements

The following are not considered SAEs:

- Situations where an untoward medical occurrence did not occur (e.g., social and/or convenience admission to a hospital, hospitalization for diagnostic tests such as CT scans).

- Anticipated day-to-day fluctuations of pre-existing disease(s) or condition(s) present or detected prior to first study treatment administration that do not worsen.
- Planned and prescheduled hospitalizations and procedures.
- Disease progression as the result of a progressive disease.

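### The SAE hospitalization criterion in 7.7 lacks the planned-only limit used in 7.2 and 7.7.2, so some unplanned admissions can be classed non-serious

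*Combined protocol and SAP*

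**What the plan says.** Section 7.7 lists six ways for an event to be serious. The hospitalization criterion carries a parenthesis: "excluding hospitalizations for study therapy, disease-related procedures, or placement of an indwelling catheter, unless associated with other SAEs". The last criterion is wider: "Includes important medical events that may not be immediately life threatening or result in death or hospitalization but may jeopardize the patient", or may need intervention to prevent one of the listed outcomes. The section closes with a default: "Adverse events that do not meet any of the above criteria for serious should be regarded as non-serious".

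Two other lists deal with admissions and procedures:

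- Section 7.2 (what is not an AE) and section 7.7.2 (what is not an SAE) each contain the bullet "Planned and prescheduled hospitalizations and procedures".
- Section 7.2 also separates a procedure from its cause. A procedure is not itself an AE, but "the condition that leads to the procedure is an AE".
- Section 7.7.2 has further exclusions with no planned limit. One covers situations without an untoward occurrence, with the examples "social and/or convenience admission to a hospital, hospitalization for diagnostic tests such as CT scans". Another is "Disease progression as the result of a progressive disease".

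Sections 7.7 and 7.7.1 require SAEs to reach the sponsor within 24 hours. Section 8.6 summarizes the number and percentage of patients with SAEs for each cohort.

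**The concern.** The three lists cover the same ground with different limits. On admissions and procedures, 7.2 and 7.7.2 turn on whether the event was planned. The 7.7 parenthesis turns on the purpose of the admission, so an emergency admission for a disease-related procedure, or for placing an indwelling catheter, falls inside it. The key phrase is undefined, and the catheter limb does not even require a link to the disease.

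Two things are at stake. Expedited reporting depends on the SAE label, so an admission that loses the label loses the 24-hour report. The SAE percentage in 8.6 is a reported safety result in a trial with no comparator (6.2), so there is no control arm in which under-counting would show. The parenthesis also asks the site to decide that the procedure is disease-related before seriousness is settled. Elsewhere the protocol wants SAEs reported whatever their cause (7.7) and treats the patient's clinical state as a matter for the causality assessment (7.5, Table 3).

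**Working it through.** The question is one of wording, and the plan gives no figure to reproduce. The check takes one event through the rules: an unplanned admission, after first dose, for a disease-related procedure or an indwelling catheter.

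1. **Is there an AE?** Yes, where an untoward condition led to the procedure. Section 7.2 makes that condition an AE. Its planned-admission bullet does not apply, because the admission was not planned.
2. **Is it serious by hospitalization?** Not on the wording of 7.7. The parenthesis covers the purpose of the admission and has no planned limit.
3. **Is it serious by another route?** There are two:
   - It meets another criterion in 7.7: death, immediate risk of death, disability, congenital anomaly or important medical event. Then it is an SAE.
   - It is associated with another SAE. The parenthesis is then lifted, and the admission counts. This does not help an event whose only claim to seriousness is the admission, since there is no other SAE for it to be associated with.
4. **Does 7.7.2 exclude it anyway?** Yes, if it is disease progression, or if nothing untoward occurred (for example an admission for a diagnostic test). Its planned-admission bullet does not apply.
5. **What remains?** An unplanned admission that passes steps 1 and 2, meets neither route in step 3 and is not excluded in step 4. The closing sentence of 7.7 makes it non-serious. With a planned-only parenthesis, the same event would be an SAE by hospitalization.

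Consequences for the events in step 5:

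- No 24-hour report (7.7, 7.7.1) and no entry in the SAE count (8.6).
- From first dose to 30 (±5) days after the last dose, the condition is still recorded as an AE (7.3.1), has its causality assessed (7.5) and enters the TEAE summaries (8.6).
- Between consent and first dose, 7.3.1 and 7.7.1 call only for SAEs to be recorded. An event classed non-serious in that interval is not recorded as an AE at all.

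Scale: a patient whose only SAE is such an admission moves the cohort percentage by 1/30 = 3.3 points if 30 patients are treated, or 1/9 = 11.1 points in a cohort closed after the first stage. These figures are per patient. They do not estimate how often it happens, and the documents give no rate of procedure-related admissions.

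**The case against.** The strongest case against the point is that the lists do not conflict. Section 7.7 defines an SAE and 7.7.2 removes further items, so a site can apply both. A reader might infer that an unplanned admission is an SAE under 7.7.2 but not under 7.7. The documents do not support that: 7.7.2 is an exclusion list, and absence from it makes nothing serious. This part of the objection stands, so the problem is a mismatch of scope and an ambiguity.

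A reader might also infer that every unplanned disease-related admission escapes, or that 7.2 and 7.7.2 remove planned events only. Neither holds. The important-medical-event criterion will catch many such admissions; an emergency admission to relieve an obstruction could readily qualify. The final clause of the parenthesis keeps in those associated with another SAE. Section 7.7.2 itself excludes diagnostic-test admissions and disease progression without a planned limit, and 7.2 treats no procedure, planned or not, as an AE in itself.

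A third inference is that the sponsor never gets to judge causality. During treatment that is too strong: the AE is recorded with its causality, and the sponsor's monitoring team reviews safety data regularly (7.1). What may be lost is the label, the expedited report and the formal assessment that 9.4.1 describes for SAEs. The screening consequence also needs a qualification. Section 5.3.1 and note q of Appendix 1 confine screening to study-related SAEs, so on that reading fewer screening events would have been recorded in any case.

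What survives is narrower. Two sites can classify the same unplanned admission differently, according to how they read an undefined phrase and how readily they invoke the important-medical-event criterion.

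**Conclusion.** The point holds in a limited form. The 7.7 carve-out is wider than the corresponding bullets in 7.2 and 7.7.2. A residual group of unplanned admissions can therefore be classed non-serious solely because of the purpose of the admission. The effect is on expedited reporting, on the descriptive SAE summary and, before first dose, on whether the event is recorded. The response-rate analysis and the two-stage rule do not use SAE counts and are not affected.

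A reader might infer that the SAE rate is biased down by a definite number of points. The direction is plausible for any event in the residual group, but the documents give no frequency, and the 39.4% SAE rate reported in section 1.1.2.5.2 for SPI-POZ-201 Cohort 1 does not separate out procedure admissions. The size is unknown and could be zero. The conclusion rests on reading the parenthesis as written, without a planned limit carried over from the other sections. This is a cheap improvement to safety reporting and does not threaten the trial's main result.

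**What to change.** In the parenthesis of the hospitalization criterion in 7.7, insert the words *planned or prescheduled* directly before *hospitalizations*, so that the limit applies to all three items. This matches the bullets in 7.2 and 7.7.2.

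Keep the final clause about association with other SAEs. Once the carve-out is limited to planned admissions, that clause still keeps complicated planned admissions in scope, so deleting it would be a step backwards. Leave the other exclusions in 7.7.2 unchanged, including disease progression. An admission attributed to progression will therefore still not count as an SAE, and this change does not address that judgement.

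The cost is two or three words, a few additional SAE reports for sites and the sponsor, and possibly a slightly higher reported SAE rate.

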7.7.1 Serious Adverse Event Reporting

From the time the study Informed Consent is signed through the first dose of study drug administration, only SAEs are to be recorded. All SAEs that occur from the first dose of study drug administration through 30 (\pm 5) days after the last dose of study treatment and SAEs that occur after 30 (\pm 5) days after the last dose of study treatment where a causal relationship with the study drug is suspected are to be reported to Spectrum within 24 hours of knowledge of the event.

SAEs are to be reported, and the serious adverse event report (SAER) faxed or e-mailed within 24 hours of knowledge of the event to the study Sponsor:

Spectrum Pharmaceuticals, Inc.
Primary Contact: Pharmacovigilance Department
[contact]
E-mail: [contact]

Spectrum may request additional information from the Investigator to ensure the timely completion of accurate safety reports. Safety data that are critical to the reportability of an SAE, such as causality assessment and serious criteria, should be included in the initial faxed or e-mailed SAER. If omitted, a timely response to drug safety data queries received from Spectrum or designee is expected.

The Investigator is to take all appropriate therapeutic measures necessary for resolution of the SAE. Any medications necessary for the treatment of the SAE are to be recorded in the concomitant medication section of the patient's CRF.

SAEs that are study-treatment related will be followed until resolution or until they have returned to Grade 1, whichever is longer, or until it is determined that the outcome will not change with further follow-up.

Additionally, the SAE is to be entered in the AE section of the CRF. Follow-up SAERs need to be submitted to Spectrum within 24 hours; once additional information regarding the event becomes available (e.g., final diagnosis is made, laboratory or test results, event course, outcome, etc).

The Sponsor or its designee will be responsible for reporting SAEs to the regulatory authorities in accordance with applicable expedited reporting regulatory guidelines. The Investigator is responsible for submitting SAEs to his/her Institutional Review Board (IRB)/Ethics Committee (EC). Copies of each SAER, and documentation of IRB/EC notification and acknowledgement of receipt will be kept in the Site's Regulatory Binder.

7.7.2 Exclusions to Serious Adverse Event Reporting Requirements

The following are not considered SAEs:

- Situations where an untoward medical occurrence did not occur (e.g., social and/or convenience admission to a hospital, hospitalization for diagnostic tests such as CT scans).

- Anticipated day-to-day fluctuations of pre-existing disease(s) or condition(s) present or detected prior to first study treatment administration that do not worsen.
- Planned and prescheduled hospitalizations and procedures.
- Disease progression as the result of a progressive disease.

7.8 Reproductive Risks

No adequate and well-controlled studies of poziotinib have been conducted in pregnant women. The effect of poziotinib on fertility and fetal development have not been studied in pregnant women. Poziotinib is not recommended for use during pregnancy.

It is not known whether taking poziotinib can cause death, serious birth defects, or other harm to unborn babies or nursing children. Patients should not become pregnant or father a child while taking part in this study.

Any pregnancy involving a study patient or a patient's partner occurs from the first dose of study treatment through 30 days after the last dose of study treatment is to be reported to the Sponsor within 24 hours after the Investigator has gained knowledge of the event via fax or e-mail (see contact information in [Section 7.7.1](#)). Pregnancies should be followed up until outcome and follow-up information regarding the outcome of the pregnancy should be faxed or e-mailed to Spectrum's Pharmacovigilance Department.

All patients who become pregnant during participation in this study will be withdrawn from the study.

8 STATISTICAL PLAN

A Statistical Analysis Plan (SAP) will be provided before data base lock.

8.1 Sample Size

The statistical analysis of each cohort will be performed separately. A total of 30 patients in each cohort will be enrolled using Simon's two-stage design. The optimal two-stage design to test the null hypothesis that $p \leq 0.050$ versus the alternative that $p \geq 0.250$ has an expected sample size of 16.76 and a probability of early termination of 0.630. If the drug is not effective, there is a 0.049 probability of concluding that it is (the target for this value was 0.050). If the drug is effective, there is a 0.098 probability of concluding that it is not (the target for this value was 0.100). For each cohort, 9 patients will be evaluated in the first stage; the cohort will be terminated if 0 respond. If the cohort goes on to the second stage, a total of 30 patients will be studied. If the total number responding is less than or equal to 3, the cohort is closed.

8.2 Method of Treatment Assignment

This study is not randomized.

8.3 Analysis Populations

The following analysis populations will be defined.

- **The Evaluable Population (EP)** consists of all enrolled patients who completed at least 6 weeks of poziotinib treatment, and have baseline and at least 1 post-baseline tumor response evaluation using RECIST, version 1.1 (and/or RANO for Cohort 4) or

progressed prior to any post-baseline image evaluation. All efficacy analyses will also be done using the Evaluable Population.

- The **Safety Analysis Population (SAF)** includes all enrolled patients who received at least 1 dose of poziotinib. All demographics, Baseline characteristics, and safety data will be analyzed using the SAF population.

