
Duration of Study: The total duration of the study will be approximately four (4) years, including enrollment and follow-up. The duration of study participation for each patient includes the following:
 
 Screening Period: Up to 30 days Treatment Period: 28 days per cycle for up to 24 months of treatment or until death, intolerable adverse events, progressive disease or other protocol-specified reasons for patient withdrawal End-of-Treatment Visit: 30 (±5) days after the last dose of poziotinib Long-Term Follow-up: After treatment period discontinuation, patients who have consented will be contacted every 3 months, for up to 2 years after patient’s first dose of poziotinib, for survival assessment. 	

Patient Replacement Strategy: Patients not efficacy evaluable i.e. not completed at least 1 cycle of poziotinib treatment and have baseline and at least 1 post-baseline tumor response evaluation using RECIST, version 1.1 (and/or RANO for Cohort 4) will be replaced unless they have discontinued from treatment or from the study due to disease progression or probable disease progression (eg. clinical progression, initiation of new therapy) or due to toxicity.
	

Study Design and Methodology
 
This is a Phase 2 multicenter, open-label study to evaluate the efficacy and safety of poziotinib in patients with EGFR or HER2 mutation-positive malignant solid tumors.
	

The study is a basket trial with five cohorts. The primary analysis will be conducted for each cohort separately. The five cohorts are:

- **Cohort 1:** Patients that have HER2-positive or HER2-negative, breast cancer with HER2 activating mutations (see **Table A**) (N=30) (See **Inclusion Criteria #4**)
- **Cohort 2:** Patients that have colorectal cancer with HER2 activating mutations (see **Table A**) (N=30)
- **Cohort 3:** Patients that have solid tumors (except NSCLC, breast cancer, or colorectal cancer) with HER2 activating mutations (see **Table A**) (N=30)
- **Cohort 4:** Patients that have GBM with EGFR activating mutations (see **Table A**) (N=30)
- **Cohort 5:** Patients that have solid tumors (except NSCLC or GBM) with EGFR activating mutations (see **Table A**) (N=30)

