- **The Evaluable Population (EP)** consists of all enrolled patients who, completed at least 1 cycle of poziotinib treatment, and have baseline and at least 1 post-baseline tumor response evaluation using RECIST, version 1.1 (and/or RANO for **Cohort 4**) or progressed prior to any post-baseline image evaluation. All efficacy analyses will be done using the **Evaluable Population**.
- The **Safety Analysis Population (SAF)** includes all enrolled patients who received at least 1 dose of poziotinib. All demographics, Baseline characteristics, and safety data will be analyzed using the **SAF** population.

Safety and Tolerability:

The following variables will be summarized and analyzed descriptively for each cohort: number of completed cycles, relative dose intensity, number and percentages of patients with TEAEs, SAEs, TEAEs leading to study drug discontinuation, TEAEs related to the study drug; and the severity of TEAEs based on CTCAE, Version 5.0.

Protocol Version/Date: Amendment 1/ 20 May 2021

Study Design Diagram

SCHEDULE OF ASSESSMENTS AND PROCEDURES

Assessment	Screening (30 days prior to Day 1, Cycle 1)	Treatment Period ^a (Each Cycle=28 [±3] Days)						End of Treatment (EOT) Visit	Long-Term Follow-up Every 3 months for 2 years
		Cycle 1 ^b			Cycle 2		Cycle 3+		
	Day -30 to Day 1	Day 1	Day 8±1	Day 15±3	Day 1	Day 8±1	Day 1	30 (±5) Days After Last Dose ^c	
Informed Consent	x								
Relevant Medical History	x								
Demographic Data	x								
Height and Weight	x	x			x		x	x	
Physical Examination ^d	x	x	x	x	x		x	x	
Vital signs	x	x	x	x	x		x	x	
ECOG Performance Status	x	x			x		x	x	
Pregnancy Test ^e	x	x			x		x	x	
Tumor Assessment	x ^f				x		x	x	
Tumor Histopathology Report ^g	x								
CBC with 5-part differential and platelets ^h	x	x	x		x	x	x	x	
Serum Chemistry ⁱ	x	x ^l			x		x	x	
Electrocardiogram (ECG) ^j	x	x	x						
Echocardiogram or MUGA Scan ^k	x								
Tissue Samples ^l	x							x	
Plasma Samples ^m	x				x		x ^l	x	
Whole Blood Sample ⁿ	x								
PK Samples ^o		x	x		x				
Dispense Poziotinib and Loperamide ^p		x			x		x		
Adverse Event Assessment	x ^q	x	x ^r	x	x	x ^r	x	x	x
Dispense and Collect Patient Diary		x	x		x	x	x	x	
Concomitant Medications review	x	x	x	x	x	x	x	x	
Telephone Contact ^s									x

- a) Each treatment cycle is 28 days with a visit window of ± 3 day. If a visit is delayed during 1 Cycle, the subsequent schedules will be delayed sequentially.

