4.3 Patient Discontinuation/Withdrawal Criteria

Patients can withdraw from participation in this study at any time, for any reason, specified or unspecified, and without prejudice.

All treated patients must be withdrawn from the study due to the following reasons:

- Development of an adverse event (AE) that interferes with the patient's participation
- Initiation of non-protocol therapy
- Development of progressive disease (PD)
- Patient withdrawal of informed consent
- Delay of poziotinib administration for >28 days since last study drug administration
- Investigator decision
- Sponsor decision

- Lost to follow-up
- Pregnancy
- Death

The reason for the patient discontinuing study treatment or terminating from the study must be recorded on the case report form (CRF). Patients who discontinue treatment or who are withdrawn from treatment will return for an End-of-Treatment Visit 30 (± 5) days after the last dose of poziotinib or prior to beginning a new treatment, whichever is first. If death is recorded as the reason for study discontinuation, the cause of death should be recorded on the CRF. Patients not efficacy evaluable i.e. not completed at least 1 cycle of poziotinib treatment and have baseline and at least 1 post-baseline tumor response evaluation using RECIST, version 1.1 (and/or RANO for **Cohort 4**) will be replaced unless they have discontinued from treatment or from the study due to disease progression or probable disease progression (eg. clinical progression, initiation of new therapy) or due to toxicity.

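### The only efficacy population requires 6 weeks of treatment in section 8.3 but 1 cycle in the synopsis, and it omits early failures, so the reported ORR can be inflated

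*Combined protocol and SAP*

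**What the plan says.** Section 8.3 defines the EP as the population that "consists of all enrolled patients who completed at least 6 weeks of poziotinib treatment". The synopsis (Analysis Populations) says that it "consists of all enrolled patients who, completed at least 1 cycle of poziotinib treatment", and a cycle is 28 days. Both versions also require a baseline and at least one later tumour evaluation, with an alternative for patients who progress before any follow-up image.

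The synopsis states: "All efficacy analyses will be done using the" EP. Section 8.3 is slightly different: "progressed prior to any post-baseline image evaluation. All efficacy analyses will also be done using the Evaluable Population". The word *also* implies a second efficacy population, but none is defined. The Safety Analysis Population (SAF: at least 1 dose) is assigned to demographics, baseline characteristics and safety.

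The replacement rule (synopsis and section 4.3) uses the 1-cycle threshold: "Patients not efficacy evaluable i.e. not completed at least 1 cycle of poziotinib treatment". Such patients "will be replaced unless they have discontinued from treatment or from the study due to disease progression or probable disease progression", and the same sentence exempts toxicity stops from replacement.

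On cohort size, section 3.1 speaks of enrolling 9 patients in stage 1. Section 8.1 speaks of enrolling 30 in total but of evaluating 9 in the first stage.

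**The concern.** The two EP definitions give different denominators for the primary endpoint from the same data. Four problems follow.

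1. Under 8.3, a patient whose progression is found on the week-4 scan is normally excluded. The synopsis wording normally keeps this patient.
2. The progression clause can be read in two ways. It may override the treatment-duration requirement, or it may replace only the scan requirement. On the second reading, early clinical progressors are also dropped, under either definition.
3. Under both definitions, a toxicity stop before 28 days without progression is outside the EP and is not replaced.
4. Section 4.3 does not say whether unreplaced patients count toward the 9 and the 30.

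Only responses confirmed about 4 weeks later count (section 8.5), so the patients removed are nearly all treatment failures. ORR is reported per cohort with a 95% CI, and that estimate would overstate activity among treated patients. PFS and OS run from treatment start, so selecting on time on treatment also removes early events from them. The SAP is due only before database lock. In an open-label study with local response assessment, that leaves the denominator open after responses are known.

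**Working it through.** **Timing.** The Schedule of Assessments (footnote f) puts the first follow-up scan at Cycle 2 Day 1, up to Cycle 2 Day 7.

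- Cycle 2 Day 1 = 28 + 1 = day 29; Cycle 2 Day 7 = day 35; with the 3-day visit window, day 38.
- Six weeks = 42 days.

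Treatment ends at first progression (section 3.1), progression requires withdrawal (section 4.3), and later dosing takes place in a separate extension study. A first-scan progressor therefore normally has fewer than 42 days of treatment. The progression clause does not help under either reading, because the progression was found on a follow-up image.

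**The plan's own design figures (section 8.1).** Inputs: n1 = 9, stop if 0 respond; n = 30, close if 3 or fewer respond; p0 = 0.05, p1 = 0.25.

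- Early termination at p0: 0.95^9 = 0.630.
- Expected N at p0: 9 + (1 − 0.630) × 21 = 16.76.
- P(success) = Σ over x = 1 to 9 of P(X1 = x) × P(X2 ≥ 4 − x), with X1 ~ Bin(9, p) and X2 ~ Bin(21, p). This is 0.0489 at p0 and 0.9019 at p1, so beta is 0.098.

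All the stated figures reproduce. The design arithmetic is sound; the problem is the denominator.

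**Reported ORR if k treated patients are dropped and not replaced.** ORR = x/(30 − k), with exact (Clopper-Pearson) 95% CI. The values of x and k are assumptions.

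| Dropped non-responders (k) | 8 responders | 4 responders (smallest successful count) |
|---|---|---|
| 0 | 8/30 = 26.7% (12.3–45.9) | 4/30 = 13.3% (3.8–30.7) |
| 1 | 8/29 = 27.6% (12.7–47.2) | |
| 3 | 8/27 = 29.6% (13.8–50.2) | 4/27 = 14.8% (4.2–33.7) |
| 6 | 8/24 = 33.3% (15.6–55.3) | 4/24 = 16.7% (4.7–37.4) |
| 9 | 8/21 = 38.1% (18.1–61.6) | |

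The direction is not strictly one-way. A patient who stops for toxicity between weeks 4 and 6 and later has a confirmed response is dropped by 8.3. If that is a seventh dropped patient, ORR is 7/23 = 30.4% (13.2–52.9).

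**DCR can move either way.** From 18/30 = 60.0%, dropping 6 uncontrolled patients gives 18/24 = 75.0%. Dropping 2 toxicity stops with stable disease at week 4 gives 16/28 = 57.1%.

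**Decision rule.** If unreplaced patients count toward the 9 and 30, the responder count is unchanged: type I error 0.049, power 0.902. If each cohort is filled to 9 and 30 evaluable patients and a fraction d of treated patients, all non-responders, is dropped, an all-treated rate of 5% becomes 0.05/(1 − d) in the EP:

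| d | EP response rate | P(success) | Early termination |
|---|---|---|---|
| 0 | 0.0500 | 0.049 | 0.630 |
| 1/30 | 0.0517 | 0.054 | 0.620 |
| 10% | 0.0556 | 0.067 | 0.598 |
| 20% | 0.0625 | 0.093 | 0.559 |
| 30% | 0.0714 | 0.133 | 0.513 |

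**The case against.** The strongest reply concerns the type I error. Section 4.3 exempts progression and toxicity stops from replacement, which most naturally means that they keep their place in the cohort, and both 3.1 and 8.1 speak of enrolling. Only the verb used for stage 1 in 8.1 points toward filling with evaluable patients. On the natural reading the stop/go rule is untouched. The error would also stay at 0.049 by construction if p were defined as the rate in the EP, which 8.1 does not specify. This stands: the error inflation is a conditional risk and should be read as one.

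The drop counts are also assumptions, and the table does not separate patients lost only to the 6-week wording from toxicity stops lost under both. If the synopsis wording governs, first-scan progressors are normally kept and the effect is smaller. This stands too; nothing in the documents allows a split.

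It can be said that reconciling the definitions is a correction, whereas moving to all treated patients is a design choice, since the protocol pairs an evaluable population with a replacement rule. But reconciliation alone leaves unreplaced toxicity stops out of the denominator.

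Finally, ORR is analysed descriptively and details are deferred to the SAP. ORR is nevertheless the primary endpoint, and no text in the protocol resolves the conflict.

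**Conclusion.** The concern holds and should be fixed. The contradiction is certain: 6 weeks in 8.3 against 1 cycle in the synopsis and the replacement rule. So is the omission of toxicity stops before 28 days without progression. The upward direction for ORR is very likely, because confirmation is required. The size is not known. With 8 responders among 30, the shift runs from under 1 percentage point (1 dropped) to about 11 points (9 dropped). An effect on type I error arises only if cohorts are filled to evaluable counts and the 5% null rate refers to all treated patients.

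**What to change.** - Delete the 6-week requirement and put one definition in 8.3 and the synopsis.
- Make the SAF, including any patients who were replaced, the primary population for ORR and DCR. Use it for PFS and OS as well, with DoR among its confirmed responders.
- For ORR, count early progression, toxicity stops and patients without a follow-up scan as non-responders unless a confirmed response is recorded. For DCR, use recorded best response, with no follow-up assessment counted as not controlled.
- State in 8.1 that patients not replaced under 4.3 count toward the 9 and the 30. State there too how replaced patients are handled in the stop/go count, so that the rule and the estimate are not left on unexplained different denominators.
- Report the 1-cycle EP as a sensitivity analysis, with the progression clause made unambiguous and first-scan progression included.
- Remove *also* from 8.3 or name the population it implies.

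The cost is wording in 8.1, 8.3, the synopsis and the SAP, with no added visits or patients. The reported ORR becomes somewhat less favourable: if 2 replaced patients enter the denominator, 8/32 = 25.0% (11.5–43.4) replaces 8/30 = 26.7%. The change belongs in the protocol now, not in an SAP written shortly before database lock.
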